#### **8.4.8 Adverse Events of Special Interest**

An adverse event of special interest (AESI) includes any non-serious conduction that falls under the system organ class (SOC) of 'Breast and Reproductive disorders'. These AESIs will be submitted to Marinus' drug safety vendor using the study specific AESI reporting form.

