#### **8.4.3      Follow-up of Adverse Events and Serious Adverse Events**

After the initial AE/SAE report, the investigator is required to proactively follow each participant at subsequent visits/contacts. All SAEs (and non-serious AEs of special interest (as defined in Section 8.4.8) will be followed until resolution, stabilization, the event is otherwise explained, or the participant is lost to follow-up (as defined in Section 7.3). Further information on follow-up procedures is provided in Section 10.4.

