### **9.2.5 Safety Analyses**

All safety analyses will be performed in the Safety Population. The results will be summarized overall and by the treatment received in the parent study (placebo or GNX).

The number and percentage of days participants received IP, the highest percentage of the maximum allowable daily dose (1800 mg or 63 mg/kg) participants received, and the total amount of IP received will be summarized.

A participant data listing will be provided with full details of the study drug dispensation.

Safety assessments include:

- AEs.
- Vital signs including BP, HR, RR, body temperature, height, and body weight.
- Physical, neurological, and developmental examinations.
- 12-lead ECG.
- Clinical laboratory tests.
- Concomitant ASM levels (as detailed in Section 8.3.6).
- C-SSRS.

Detailed analysis and complete listings will be outlined in the SAP.

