### **9.2.6 Subgroup Analysis**

The following subgroup summarizations of the efficacy parameter are planned as outlined in the SAP:

- Gender (Female vs Male).
- Age groups (1 to 6 years; 7 to 12 years; 13 to 17 years; and 18 years and above).

All the analyses will follow the rules:

- The results will be presented overall, for participants previously enrolled in Study 1042-TSC-2001, and for participants previously enrolled in Study 1042-TSC-3001 results will also be classified according to the double-blind treatment received by participants in Study 1042-TSC-3001.
- The seizure endpoints will be derived starting from the first dosing day of OLE treatment.
- No per protocol analyses will be performed

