## 4. STATISTICAL METHODOLOGY

### 4.1. General Methodology

Unless otherwise stated, SAS®software (Version 9.4 SAS Institute Inc, Cary, NC) will be used for the generation of all tables, graphs, and statistical analyses. Summary statistics including the number of subjects (n), mean, standard deviation, median, minimum and maximum will be presented for continuous variables. Generally, the minimum and maximum values will be presented to the same decimal precision as the raw values, the mean and median values to one more, and the standard deviation, to two more decimal places than the raw values. For categorical variables, per category, the absolute counts (n) and percentages (%) of subjects with data, and if appropriate, the number of subjects with missing data, will be presented. Percentages will be presented to one decimal place.

For AEs, medical history and concomitant medications reported on a per-subject basis, the denominator for the percentage calculation will be the number of subjects in each treatment group. A subject will be considered at risk if the subject is in the analysis set and in the subgroup of interest.

If a p-value is less than 0.0001 it will be displayed as “< 0.0001”. All p-values larger than 0.0001 will be rounded to 4 decimal places.

The results of the primary and secondary endpoints will be summarized separately. The results will be summarized by the treatment received by participants in the parent study. Participant demographics, characteristics, and medical history at randomization or the start of the parent study will be summarized using descriptive statistics.

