### 4.3. Statistical Methods for Primary Safety Analyses

#### 4.3.1. Adverse Events

Adverse events (AEs) are collected from the time of informed consent/assent through the defined follow-up period. AEs are coded using MedDRA dictionary, version 24.0 and are

categorized by system organ class (SOC) and preferred term (PT). A treatment-emergent AE (TEAE) is defined as an AE that starts or worsens on or after the first day of dosing with IP. Detailed by-patient listings of all AEs reported during the study will be provided and will include verbatim and coded terms for each AE.

For the safety Analysis Set, the following tabular summaries will be created:

- An overall summary of TEAEs will present the number and percentage of subjects with at least 1 reported TEAE, study drug related TEAE, serious TEAE, TEAE of Grade 3 or higher, study drug infusion interruption, and death
- TEAEs by system organ class and preferred term
- TEAEs by system organ class, preferred term, and maximum severity
- Study drug related TEAEs by system organ class and preferred term
- TEAEs by decreasing frequency of preferred term
- Moderate or severe TEAEs by system organ class and preferred term
- Moderate or severe study drug related TEAEs by system organ class and preferred term
- TEAEs that led to study drug infusion interruption by system organ class and preferred term
- Serious TEAEs by system organ class and preferred term
- Serious study drug related TEAEs by system organ class and preferred term

For incidence reporting, if a subject reported more than 1 AE that was coded to the same preferred term/system organ class, the subject will be counted only once for that specific preferred term/system organ class. For TEAEs presented by severity, the worst severity for each event during the clinical trial will be presented for each subject. If the severity is missing for a TEAE, then a severity of “Severe” will be assigned. The imputed values for severity assessment will be used for incidence summaries, while the actual values will be used in data listings.

For TEAEs presented by relationship to study drug, the closest relationship to study drug for each event during the clinical trial will be presented for each subject. If the relationship to investigational product is missing for a TEAE, a causality of “Related” will be assigned. The imputed values for relationship assessment will be used for incidence summaries, while the actual values will be presented in data listings.

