All AEs, SAEs, TEAEs leading to study drug interruption, and SAEs leading to death will be displayed in separate listings.

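### Breast and reproductive events are the only AESI, yet the SAP plans no AESI summary and divides sex-specific events by both sexes, so those percentages come out about half their size under a 50:50 split

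*Protocol*

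**What the plan says.** Protocol 8.4.8 names one AESI class and gives it a study-specific reporting form: "An adverse event of special interest (AESI) includes any non-serious conduction that falls under the system organ class (SOC) of" breast and reproductive disorders. Protocol 8.4.3 gives these events the same follow-up as serious ones: "All SAEs (and non-serious AEs of special interest (as defined in Section 8.4.8) will be followed until resolution". For the analysis, protocol 9.2.5 defers to the SAP: "Detailed analysis and complete listings will be outlined in the SAP".

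SAP 4.3.1 sets out ten tabular summaries of treatment-emergent events. None is for AESIs, and the term does not occur in the SAP. The summary that would carry these events is "TEAEs by system organ class and preferred term". The listings are equally general: "All AEs, SAEs, TEAEs leading to study drug interruption, and SAEs leading to death will be displayed in separate listings".

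On percentages, SAP 4.1 states that "the denominator for the percentage calculation will be the number of subjects in each treatment group". The next sentence adds: "A subject will be considered at risk if the subject is in the analysis set and in the subgroup of interest". The Safety Analysis Set (SAP 4.2) is every dosed participant, with no restriction by sex or age. Gender and age bands are planned for efficacy only. Protocol 9.2.6 introduces them with "The following subgroup summarizations of the efficacy parameter are planned as outlined in the SAP", and SAP 4.4.1 and 4.4.2 apply them to seizure frequency and responders.

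**The concern.** Many events in this class, menstrual and male genital events for instance, can occur in only one sex. Under the rule in SAP 4.1, each such preferred term is divided by a column total that includes the other sex. The resulting percentage is not the incidence among people who could have had the event, and it is always lower than that incidence.

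The incidence of adverse events is the first item among the primary endpoints (protocol section 3, SAP 2.3.1), and SAP 3.2 makes the whole study descriptive. The tabulated percentages are therefore the result itself. The one class picked out in advance for special reporting and follow-up is also the class where an all-participant denominator fits worst, and no planned table corrects for it.

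**Working it through.** **No plan figure to reproduce.** Neither document gives an AESI rate, a sex split or a share of participants past puberty. The check is a ratio of denominators.

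**Inputs**
- Planned enrolment: N = 169 (protocol 9.4) and N = 150 (SAP 3.1). The two differ, so both are used.
- Female share f: not in the documents. Assumed 0.50, with a range of 0.40 to 0.60.
- Participants with a female-only event: x = 3, for illustration.

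**Formulas**
- Percentage under SAP 4.1: x / N
- Percentage among females: x / (f × N)
- Understatement factor: [x / (f × N)] ÷ [x / N] = 1 / f. It depends on neither N nor x.
- For a male-only event, replace f by 1 − f.

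**Factor**
- f = 0.40: 1/0.40 = 2.50 for female-only events, 1/0.60 = 1.67 for male-only events
- f = 0.50: 1/0.50 = 2.00 for both
- f = 0.60: 1.67 for female-only events, 2.50 for male-only events

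**Example at f = 0.50**
- N = 169: 3/169 = 1.8%. Females: 0.5 × 169 = 84.5, taken as 84; 3/84 = 3.6%.
- N = 150: 3/150 = 2.0%. Females: 0.5 × 150 = 75; 3/75 = 4.0%.

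**Same example over the assumed range**
- N = 169: 3/68 = 4.4% at 40% female, 3/101 = 3.0% at 60% female, against 1.8% reported.
- N = 150: 3/60 = 5.0% at 40% female, 3/90 = 3.3% at 60% female, against 2.0% reported.

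Results are also shown by parent-study treatment. The same formula applies in each column, with that column's own sex split.

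**Does the at-risk sentence in SAP 4.1 already solve this?** It ties being at risk to a subgroup of interest. It would give a sex-specific denominator only if sex were a defined subgroup for adverse events. Protocol 9.2.6, SAP 4.4.1 and SAP 4.4.2 define gender and age subgroups for efficacy alone, and SAP 4.3.1 defines none. A programmer following the text would use the column total.

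**The case against.** The strongest defence is that the SAP does not depart from the protocol. AESI is a reporting and follow-up category there. It is not an objective or an endpoint, and protocol 9.2.5 does not include it in its list of safety assessments. Because the AESI is one entire organ class, that class's row in the general table already gives its count. Sex is summarised for the Safety Population (SAP 5.3) and every adverse event is listed by patient, so a reader could rebuild a rate by sex. The table shells are a separate document (SAP section 8) and may add detail. All of this stands, and it limits the consequence to how incidence is presented. It does not correct the percentages that the SAP's stated rule will produce.

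Three stronger readings are tempting, and the documents do not support them:

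- *The dilution is at least two-fold.* That would need a sex split that neither document gives. For the majority sex the factor is below 2 (1.67 at 60%). Nor need every event in the class be sex-specific.
- *The dilution is four-fold or more once puberty counts.* At 50:50, if half of the relevant sex were past puberty, the arithmetic gives 1/(0.5 × 0.5) = 4. The documents do not give that share, and a denominator by sex alone would still include young children.
- *Serious events in the class are left out because protocol 8.4.8 covers only non-serious ones.* No planned output counts from the AESI form. The general SAP 4.3.1 table combines serious and non-serious events, and serious events also have their own table.

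**Conclusion.** The point holds as a gap in the SAP with a modest, calculable effect, and it should be closed. No AESI summary is planned, and the stated denominator includes both sexes for events that only one can have. The at-risk sentence shows that the SAP accepts the principle of an at-risk denominator but does not apply it by sex to adverse events.

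The understatement for a sex-specific preferred term is about two-fold under an assumed 50:50 split, or 1.7 to 2.5 if 40 to 60% are female. These factors rest on that assumption and should be replaced by the actual split, which the sponsor holds. Counts remain in the tables and listings. With everything descriptive, no test, power figure or error rate changes.

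**What to change.** Add two rules to SAP 4.3.1:

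1. All treatment-emergent events in the breast and reproductive organ class, serious and non-serious together, are summarised by preferred term separately for females and males. The denominator is the number of that sex in the Safety Analysis Set, within each column shown.
2. Sex-specific preferred terms in the other adverse event tables use the same denominator, with a footnote. The list of such terms is fixed before the database is locked.

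If rates in participants past puberty are wanted, present the first table also by the age bands already in protocol 9.2.6 and SAP 4.4.1. The denominator by sex does not do this alone, and the bands are only a proxy for puberty.

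Protocol 8.4.8 needs no amendment. Its limit to non-serious events governs the reporting form, and no planned table depends on it.

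The cost is one extra table and a denominator rule, made through the SAP amendment route in SAP section 6. Sex is already summarised under SAP 5.3, so no new data are needed. The downside is smaller denominators, so each percentage is less precise and moves more with a single event.

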#### **8.4.9 Pregnancy**

Details of all pregnancies in female participants and, if indicated, female partners of male participants are to be reported from the time informed consent is signed until the defined follow-up period.

Any report of pregnancy for any female study participant or the partner of a male study participant must be reported within 24 hours to the Marinus' drug safety vendor or its delegate using the Pregnancy Report Form. A copy of the Pregnancy Report Form (and any applicable follow-up reports) must also be sent to the CRO/Marinus medical monitor using the details specified in the emergency contact information section at the beginning of the protocol. The pregnant female study participant must be withdrawn from the study.

Every effort should be made to gather information regarding the pregnancy outcome and condition of the infant. It is the responsibility of the investigator to obtain this information within 30 calendar days after the initial notification and approximately 30 calendar days after delivery.

Pregnancy complications such as spontaneous abortion/miscarriage or congenital abnormality are considered SAEs and must be reported as outlined in Section 10.4 of the protocol using the Marinus Clinical Study Serious Adverse Event Form. Non serious AEs are to be reported as per clinical eCRF guidelines. Note: An elective abortion is not considered an SAE.

Any poststudy pregnancy-related SAE considered reasonably related to the study intervention by the investigator will be reported to the sponsor as described in Section 8.4.4. While the investigator is not obligated to actively seek this information in former study

participants/pregnant female partner, he or she may learn of an SAE through spontaneous reporting.

In addition to the above, if the investigator determines that the pregnancy meets serious criteria, it must be reported as an SAE to Marinus' drug safety vendor as outlined in Section 10.4 of the protocol using the Marinus Clinical Study Serious Adverse Event Form. The test date of the first positive serum  $\beta$ -human chorionic gonadotropin test or ultrasound result will determine the pregnancy onset date.

Any female participant who becomes pregnant while participating in the study will discontinue study intervention and be withdrawn from the study.

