#### **4.4 End of Study Definition**

**End of Study (Individual Patient):** A participant is considered to have completed the study if they have completed all study visits up to and including Visit 14 (Week 160) (Table 1).

A participant is considered to have ended their participation when they either complete the study, or when they withdraw and complete the Early Termination visit.

**End of Study (End of Trial):** The end of the study is defined as the date of the last visit of the last participant in the study or last scheduled procedure shown in the Schedule of Activities (SOA; Table 1) for the last participant in the study globally.

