# **7 DISCONTINUATION OF STUDY INTERVENTION AND PARTICIPANT DISCONTINUATION/WITHDRAWAL**

## **7.1 Discontinuation of Study Intervention**

In rare instances, it may be necessary for a participant to permanently discontinue study intervention. If the IP is discontinued at any time, participants should follow the 2-week taper schedule unless otherwise medically indicated such, as drug-induced rash. If the participant discontinues the IP, evaluations listed for the Early Termination Visit (Visit 13 [Week 156]; as shown in the SOA [Table 1]) are to be performed as completely as possible along with the end of study and safety follow-up assessment, as appropriate. Comments (spontaneous or elicited) or complaints made by the participant must be recorded in the source documents. The reason for termination, date of stopping IP, and total amount of IP taken must be recorded in the eCRF and source documents. Discontinuation of IP due to AEs must also be reflected on the AE eCRF page. Participants who discontinue IP should undergo a 2-week or shorter taper period, as clinically indicated. These participants will have a visit 2 weeks after the end of taper to complete the safety follow-up assessments.

The reason for early discontinuation of the IP must be determined by the investigator and recorded in the participant's source documents and on the eCRF. If a participant is withdrawn for more than 1 reason, each reason should be documented in the source document and the most clinically relevant reason should be entered on the eCRF.

Reasons for early termination include but are not limited to the following:

- AE (including pregnancy).
- Protocol violation/protocol deviation.
- Withdrawal by participant or parent(s)/LAR(s).
- Lost to follow-up.
- Lack of efficacy.
- Death.
- Investigator decision.

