## 7.2 Discontinuation/Withdrawal from the Study

All participants or his/her parent(s)/LAR(s) reserve the right to withdraw from the study at any time, as stated in the informed consent/assent form. The investigator may discontinue participants from the clinical study for any of the following reasons:

- Participant is found to have entered the study in violation of the protocol.
- Participant requires the use of a disallowed concomitant medication.
- Participant's condition changes after entering the clinical investigation so that the participant no longer meets the inclusion criteria or develops any of the exclusion criteria.
- Participant or parent(s)/LAR(s) withdraws consent or assent to participate in the study.
- Participant is noncompliant with the procedures set forth in the protocol.
- Participant experiences an AE/SAE that warrants withdrawal from the study.
- Any laboratory, medical, or clinical finding for which clinical intervention should take precedence over study participation. This includes:
  - Aspartate aminotransferase (AST)/serum glutamic oxaloacetic transaminase (SGOT) or alanine aminotransferase (ALT)/serum glutamic pyruvic transaminase (SGPT)  $> 3 \times$  upper limit of normal (ULN).
  - Total bilirubin levels  $> 1.5 \times$  ULN.
  - Estimated glomerular filtration rate (eGFR)  $< 30$  mL/min.
- It is the investigator's opinion that it is not in the participant's best interest to continue in the study.

Decisions to discontinue the study will be made at each participating site by the investigator. If feasible, the reason for discontinuation should be discussed with the sponsor's medical monitor prior to participant's discontinuation.

At the time of discontinuing from the study, if possible, an Early Termination Visit (Visit 13 [Week 156]) should be conducted as shown in the SOA (Table 1). At this visit, participants will start a 2-week taper and then return to the site 2 weeks later for safety follow-up assessments.

If the participant withdraws consent for disclosure of future information, the sponsor may retain and continue to use any data collected before such a withdrawal of consent.

If a participant withdraws from the study, he/she may request destruction of any samples taken and not tested, and the investigator must document this in the site study records.

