### **8.1.3 Safety Follow-up**

A safety follow-up visit will be conducted at Visit 14 (Week 160), which will be 2 weeks after the end of the 2-week taper for participants who are not continuing commercially available GNX (Table 1). This will be the end of study visit for these participants.

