## **10.5 Appendix 5: Contraceptive and Barrier Guidance**

### **10.5.1 Female Contraception**

WOCBP must be using a medically acceptable form of birth control and have a negative quantitative serum  $\beta$ -HCG test collected at the initial visit. WOCBP must be advised to use medically acceptable birth control throughout the study period and for 30 days after the last dose of IP. These include intrauterine devices, hormonal contraceptives (eg, combined oral contraceptives, patch, vaginal ring, injectables, and implants), and surgical sterilization (such as oophorectomy or tubal ligation). When used consistently and correctly, "double-barrier" methods of contraception can be used as an effective alternative to highly effective contraception methods (see Section 10.5.3 for "double-barrier methods"). Contraceptive measures such as Plan BTM, sold for emergency use after unprotected sex, are not acceptable methods for routine use.

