### **10.5.2 Male Contraception**

Male participants must agree to use highly effective contraceptive methods during the study and for 30 days after the last dose of IP. Highly effective methods of contraception include surgical sterilization (such as a vasectomy) and adequate "double-barrier" methods as described in Section 10.5.3.

Male participants should not donate sperm during the study and for 30 days after the last dose of IP.

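### The pregnancy reporting window in Section 8.4.9 has no stated length and, on the full-taper schedule, ends about 16 days before the protocol's own 30-day contraception period

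*Protocol*

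**What the plan says.** **Reporting window.** Protocol Section 8.4.9 says that details of pregnancies in female participants and, if indicated, in female partners of male participants "are to be reported from the time informed consent is signed until the defined follow-up period". The section gives no length for that period. It then requires any report of pregnancy to be sent within 24 hours, and that sentence has no end date. It asks for every effort to obtain the pregnancy outcome and the infant's condition. For the time after the study it names only pregnancy-related SAEs judged reasonably related to the intervention, and the investigator need not look for them.

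**Follow-up visit.** Section 8.1.3 names Visit 14 (Week 160) as the safety follow-up and places it as follows: "which will be 2 weeks after the end of the 2-week taper for participants who are not continuing commercially available GNX". Section 7.1 says of those who discontinue: "These participants will have a visit 2 weeks after the end of taper to complete the safety follow-up assessments". Table 1 gives the visit a window of plus or minus 3 days. Section 7.2 is worded differently: "At this visit, participants will start a 2-week taper and then return to the site 2 weeks later for safety follow-up assessments".

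**Contraception period.** Section 10.5.1 advises women of childbearing potential to use birth control "throughout the study period and for 30 days after the last dose of IP". Criterion 5 in Section 5.1 does not state those 30 days for women. For men, criterion 6 in Section 5.1 and Section 10.5.2 both set 30 days, and Section 10.5.2 adds: "Male participants should not donate sperm during the study and for 30 days after the last dose of IP".

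**Testing.** Section 8.3.8 and footnote f of Table 1 require a serum test at Visit 1, then home urine tests every 4 weeks during the OLE. The pregnancy-test row of Table 1 is marked only at Visit 1.

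**The concern.** The protocol treats the 30 days after the last dose as a period in which pregnancy should be avoided, yet its collection of pregnancies appears to stop about halfway through. A pregnancy beginning in the later part falls outside the stated window, and no procedure is designed to find it.

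Pregnancies conceived earlier can be affected too. Section 8.4.9 dates onset by the first positive serum test or ultrasound, not by conception. A pregnancy conceived during dosing or soon after it, but confirmed after Visit 14, is therefore dated outside the window.

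Safety is the primary objective, and Section 8.4.9 itself wants maternal and infant outcomes followed. Because the window is not given in days, sites can also close it at different times.

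**Working it through.** No sample-size or power formula applies. The check is date arithmetic.

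**Inputs**
- Visit 13 at Week 156 (Table 1)
- Taper of 2 weeks, which may be shortened (Sections 4.1, 6.2, 7.1)
- Follow-up 2 weeks after the end of the taper (Sections 7.1, 8.1.3)
- Visit 14 window of plus or minus 3 days (Table 1)
- Contraception to 30 days after the last dose (Sections 5.1 for men, 10.5.1, 10.5.2)

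**Step 1: reproduce the plan's own figure.** 156 + 2 + 2 = Week 160, which matches Section 8.1.3.

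**Step 2: days from last dose to follow-up.** With a full taper the last dose falls at Week 156 + 2 = Week 158. Then (160 − 158) × 7 = 14 days. With the visit window this is 11 to 17 days.

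**Step 3: uncovered days = 30 − days from last dose to follow-up.**

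| Visit 14 timing | Days after last dose | Uncovered days | Share of 30 |
|---|---|---|---|
| 3 days early | 11 | 19 | 63% |
| On schedule | 14 | 16 | 53% |
| 3 days late | 17 | 13 | 43% |

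**Step 4: other readings of the follow-up date**
- *Section 7.2 taken literally.* The taper starts at the Early Termination Visit and the participant returns 2 weeks later. Follow-up is then 14 − 14 = 0 days after the last dose, leaving up to 30 days uncovered.
- *No taper, visit still 4 weeks after Visit 13.* Follow-up is at day 28 and 30 − 28 = 2 days are uncovered (5 to none with the window).
- *No taper, visit 2 weeks after stopping.* Follow-up is at day 14 and 16 days are uncovered.

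**Step 5: does testing close the gap?** Home tests every 4 weeks fall nominally on Week 156 (156/4 = 39) and Week 160 (160/4 = 40), so a completer may have a test at about day 14 although Table 1 marks none there. The text does not say whether the testing period includes Week 160. Early discontinuers need not be on that cadence. A test at day 14 cannot detect a conception on days 15 to 30, and no test is planned for partners of male participants.

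**The case against.** A reader might infer that pregnancies in the later half of the 30 days go unreported, are lost from the safety record, or are never followed to outcome. The documents do not support that. The 24-hour sentence in Section 8.4.9 covers any report of pregnancy and carries no end date. The same section asks for outcome information to about 30 days after delivery, well beyond Visit 14. Section 8.4.1 requires related SAEs discovered at any interval after the study to be reported. These points stand. What remains is that the 24-hour sentence governs reports that arrive and asks nobody to look, and that an uncomplicated pregnancy is not covered by the SAE clauses.

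A reader might also take 16 days as a firm figure for every woman of childbearing potential and every man with a partner. It is an inference from an undated period and it depends on the taper. Section 8.1.3 ties Visit 14 to participants not continuing commercially available GNX, and partner pregnancies are collected only if indicated. The empty cells in Table 1 do not prove that testing stops before Visit 13.

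Finally, nothing in the protocol requires the reporting and contraception periods to match, and the pregnancy window uses the same follow-up wording as AEs and SAEs. It is fair to call this a design choice. But the protocol sets its own 30-day period, and leaving part of it outside the window gains nothing the documents describe.

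**Conclusion.** The mismatch holds as a gap in active ascertainment. With a full 2-week taper and follow-up 2 weeks after it, the stated window ends about 14 days after the last dose. About 16 of the 30 contraception days (13 to 19 with the visit window) then lie outside it, and pregnancies arising in them are not actively sought.

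This rests on reading the defined follow-up period as ending at Visit 14, the only follow-up the protocol schedules. Across the readings of Section 7.2 and an omitted taper, the gap runs from about 2 to 30 days. The 53% is a share of days, not of pregnancies; the documents give no expected number of pregnancies, so the number affected cannot be estimated. The point is a cheap improvement to safety capture, not a failure of the design.

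**What to change.** - In Section 8.4.9, state the end of the reporting window in days from the last dose so that it covers the protocol's own 30-day contraception period. Include pregnancies conceived in that period but confirmed later. Apply it to female participants and, if indicated, to partners of male participants.
- Reconcile Sections 7.1, 7.2 and 8.1.3 on when the safety follow-up occurs, and say what applies to participants who continue on commercially available GNX.
- At the last visit, tell participants to report a pregnancy confirmed later. Where feasible, add one brief remote contact at or shortly after day 30. Section 10.1.7 already lets telephone visits be done by secure e-mail where the site's IRB/IEC allows it.

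The cost is a small amount of protocol wording and one short contact for the participants concerned. The downside is that the contact falls after the last visit, about 2 weeks later with a full taper. It can also miss very recent conceptions, which is why the instruction to report later confirmations is needed as well.
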